3.1.1. Order of Assessments

It is important that PK sampling occurs as close as possible to scheduled time. In order to achieve this, other assessments scheduled at the same time may be initiated prior to the time point. Another aspect for the proposed timing is that physiological assessments such as heart rate or blood pressure as well as inquiring for AEs should not be accidentally influenced by physical interventions such as a venous puncture. The sequence at a particular time point is:

- 1 Electrocardiograms
- 2 Vital signs (blood pressure and pulse)
- 3 Pharmacokinetic blood sampling

Details of acceptable tolerance windows for safety, PK and PD assessments will be included in a WAD which will be agreed upon and signed off before the start of the study. Participants should be counseled to be available for repeat sampling within the windows of allowance, if required.

3.1.2. End of Study

The end of study is defined as the last participant's last visit to the study Clinical Unit.

3.1.3. Expected Duration of the Study

Each participant will be involved in the study for approximately 1 year.

3.2. Rationales for Study Design and Dose Selection

3.2.1. Rationale for Study Design

An open label, parallel group design has been chosen for this single dose PK comparability study.

The study will assess PK comparability between different formulations of AZD7442, which is a combination of two individual mAbs, AZD8895 and AZD1061. The materials to be assessed will be:

- A co-formulation of clonal cell line material of AZD8895 + AZD1061 mAbs as a single IM injection from a single mixture,
- Individual formulations of clonal cell line material of AZD8895 and AZD1061 mAbs as separate sequential IM injections, and
- Individual formulations of cell pool material of AZD8895 and AZD1061 mAbs as separate sequential IM injections.

3.2.2. Dose Rationale

The 300 mg (total protein) IM dose selected for investigation in this study is the anticipated therapeutic dose for prophylaxis of COVID-19. The data generated on the 300 mg IM dose is also expected to support a single IM dose of 600 mg for treatment of mild to moderate COVID-19 as the 600 mg dose (co-formulation) will be administered as two IM injections of 300 mg each.

3.3. Risk-benefit Assessment

Detailed information about the known and expected benefits and potential risks of AZD7442 may be found in the IB.

3.3.1. Description of AZD7442

AZD7442 is a combination product of two mAbs: tixagevimab (AZD8895) and cilgavimab (AZD1061) that are neutralizing mAbs that bind specifically to the RBD of the SARS-CoV-2 spike protein. Neither mAb has any human target. There are no potential risks based on mechanism of action.

3.3.2. Clinical Pharmacokinetics

Measured serum AZD8895 and AZD1061 concentrations support that the PK of these mAbs are similar to each other and are consistent with what has been observed for another IgG1 κ mAb that has been engineered to include YTE amino acid substitutions to extend the half-life ([Griffin et al 2017](#)). Therefore, the half-life of AZD7442 is estimated to be approximately 90 days which will allow for long-term protection.

3.3.3. Adverse Events, Contraindications and Warnings

Potential risks of AZD7442 are those that are associated with the administration of any immunoglobulin, including polyclonal immunoglobulin preparations and mAbs. The important potential risks associated with the administration of immunoglobulin, include, but are not limited to, anaphylaxis and other serious hypersensitivity reactions including immune complex disease. Other potential risks include, but are not limited to, injection site reactions, infusion-related reactions, and ADE disease.

Antibody-dependent enhancement of disease is a theoretical risk. Two different syndromes exist:

- 1 Antibody-dependent enhanced disease that involves increased binding efficiency of virus-antibody complexes to Fc receptor bearing cells and which triggers virus entry. The mAbs in AZD7442 have been designed with a modification to prevent binding to cellular Fc receptors, so the risk of antibody-dependent enhanced disease occurring via this mechanism should range from very low to none.

2 Vaccine-associated enhanced respiratory disease, which is a distinct clinical syndrome that occurred in young children in the 1960s when whole inactivated virus vaccines for measles and RSV were tested.

Immunizing with limiting doses of RSV antigen, especially with conformationally incorrect antigens, can result in two major types of immunological phenomena:

- A relatively high ratio of antibody that binds but does not neutralize the virus could potentially result in immunogenic cell death and complement activation (leading to inflammation and airway obstruction).
- Immunization with whole inactivated virus vaccines can result in allergic inflammation characterized by reactions such as increased mucus production, airway hyperresponsiveness, and attenuated cytolytic T cell activity (T helper 2 cell immune response). This mechanism, induced by vaccines, are not expected to be provoked by mAbs.

There are no identified risks associated with AZD7442. No observations are considered to represent expected adverse reactions that would form part of an emerging safety profile.

Refer to the IB for the most up to date study safety findings with regards to completed AZD7442 administration.

4. STUDY POPULATION

4.1. Selection of Study Population

The investigator should keep a participant screening log of all potential participants who consented and were subjected to screening procedures.

Participants who fail to meet the inclusion criteria or any exclusion criterion should not, under any circumstances, be randomized or dosed in the study. There can be no exceptions to this rule.

This study will be conducted in male and female participants. The study may not necessarily be balanced regarding gender. The study was not formally powered to detect differences between genders for the primary endpoint. It is not planned to perform sub-analyses on gender.

4.1.1. Inclusion Criteria

For inclusion in the study participants should fulfill the following criteria:

- 1 Provision of signed and dated, written informed consent prior to any study specific procedures.
- 2 Male and female participants, aged 18 years and older, vaccinated or non-vaccinated against SARS-CoV-2, with suitable veins for cannulation or repeated venipuncture. Vaccinated participants should have received their last dose of the vaccine at least 14 calendar days before IMP administration (Day 1).
- 3 Healthy participants according to medical history, physical examination, and baseline safety laboratory tests, according to the judgment of the investigator.
- 4 Documented negative results of a SARS-CoV-2 RT-PCR test collected \leq 3 days prior to IMP dose administration (Day 1) or a negative rapid SARS-CoV-2 antigen test on Day 1 (pre-dose) NOTE: A negative SARS-CoV-2 RT-PCR retest result or a negative rapid SARS-CoV-2 antigen test is required if participant has symptoms of infection or has any known/suspected exposure after the initial SARS-CoV-2 RT-PCR test. Participants who do not meet this criterion may be re-screened more than once and up to a maximum of two times as per investigator discretion but with prior approval of the Medical Monitor.
- 5 Able to complete the Follow-up Period up to Day 361 as required by the protocol.
- 6 Electrocardiogram without clinically significant abnormalities at screening.
- 7 Body weight \geq 50 kg to \leq 110 kg at screening and a BMI \geq 18.0 to \leq 30 kg/m² at the time of the Screening Visit.
- 8 All participants must adhere to the contraception methods details in Section 4.2.1.

- (1) Male participants: to avoid the transfer of any fluids to a sexual partner, all male participants must use a condom from Day 1 and agree to continue through 90 days following administration of the study intervention.
- (2) Female participants: Female participants of childbearing potential should be willing to use a highly effective form of birth control from Day 1 up to Day 361. These must include the use of at least one highly effective form of birth control. Women not of childbearing potential are defined as women who are either permanently sterilized (hysterectomy, bilateral oophorectomy, or bilateral salpingectomy), or who are postmenopausal.

4.1.2. Exclusion Criteria

Participants will not enter the study if any of the following exclusion criteria are fulfilled:

- 1 Known history of allergy or reaction to any component of AZD7442 (AZD8895 + AZD1061).
- 2 Previous hypersensitivity, or severe adverse reaction following IM administration of a mAb.
- 3 Significant infection or other acute illness, including fever $> 100^{\circ}\text{F}$ ($> 37.8^{\circ}\text{C}$) on the day prior to or day of randomization. Participants excluded for transient acute illness may be dosed if illness resolves within the 28-day Screening Period. Otherwise, the participant will be reported as a screen failure.
- 4 History of infection with SARS or Middle East Respiratory Syndrome.
- 5 Positive SARS-CoV-2 result based on available data at screening or at Day 1.
- 6 Any clinical signs and symptoms consistent with COVID-19, eg, fever, dry cough, dyspnea, sore throat, fatigue, or confirmed infection by appropriate laboratory test within the last 4 weeks prior to screening or on admission.
- 7 History of malignancy.
- 8 History of clinically significant bleeding disorder (eg, factor deficiency, coagulopathy, or platelet disorder), or prior history of significant bleeding or bruising following IM injections or venipuncture.
- 9 Active infection with hepatitis B or C or positive test for hepatitis C or for hepatitis B surface antigen at screening.
- 10 Immunodeficiency due to illness, including HIV infection, or due to drugs, including any course of glucocorticoid therapy exceeding 2 weeks of prednisone or equivalent at a dose of 20 mg daily or every other day within 6 months prior to screening. HIV testing must be negative at screening.
- 11 History of alcohol or drug abuse within the past 2 years that, according to the investigator, might affect assessments of safety or ability of the participant to comply with all study

requirements OR positive urine drug or alcohol at screening, and positive breathalyzer test at randomization. Excessive intake of alcohol defined as the regular consumption of more than 24 g of alcohol per day for men or 12 g of alcohol per day for women.

- 12 Any other significant disease, disorder, or finding that may significantly increase the risk to the participant because of participation in the study, affect the ability of the participant to participate in the study, or impair interpretation of the study data.
- 13 Aspartate aminotransferase, ALT, or serum creatinine above $2 \times$ the ULN; bilirubin and ALP $> 1.5 \times$ ULN.
- 14 Any laboratory value in the screening panel that, in the opinion of the investigator, is clinically significant or might confound analysis of study results.
- 15 Pregnant or nursing female.
- 16 Any condition that, in the opinion of the investigator, might compromise participant safety or interfere with evaluation of the IMP or interpretation of participant safety or study results.
- 17 Employees of the sponsor, clinical study site, or any other individuals involved with the conduct of the study, or immediate family members of such individuals.
- 18 Any drug therapy within 7 days or 5 drug half-lives (whichever is longer) prior to Day 1 (except contraceptives or a single use of acetaminophen, aspirin, antihistamine, or combination OTC product that contains acetaminophen with an antihistamine, or OTC nonsteroidal anti-inflammatory agent at a dose equal to or lower than that recommended on the package). Routine vaccines within 14 days prior to Day 1. Vitamins and other nutritional supplements that are not newly introduced, ie, have been taken for at least 30 days prior to screening, are not exclusionary.
- 19 Receipt of Ig or blood products within 6 months prior to screening.
- 20 Any prior receipt of another mAb indicated for the prevention or treatment of SARS-CoV-2 or COVID-19. NOTE: Participants are permitted to receive anti-COVID-19 vaccination during study. Participant vaccination status will be documented throughout the study in the eCRF.
- 21 Receipt of a mAb within 6 months or 5 antibody half-lives (whichever is longer) prior to screening.
- 22 Receipt of any investigational product within 90 days or 5 half-lives (whichever is longer) prior to Day 1 or expected receipt of investigational product during the Follow-up Period, or concurrent participation in another interventional study.
- 23 Blood drawn in excess of a total of 450 mL (1 unit) for any reason within 30 days prior to randomization.
- 24 Plasma donation within 1 month of screening or any blood donation/loss more than 500 mL during the 3 months prior to screening.
- 25 Participants who cannot communicate reliably with the investigator.

- 26 Vulnerable participants, eg, kept in detention, protected adults under guardianship, trusteeship, or committed to an institution by governmental or juridical order.
- 27 Receipt of a COVID-19 vaccination \leq 14 days before IMP administration (Day 1) or plan to receive a COVID-19 vaccination \leq 14 days after IMP dose (such participants can subsequently be included in the study once they have reached $>$ 14 days after their last dose of vaccine).

4.2. Restrictions During the Study

The following restrictions apply for the specified times during the study period:

- 1 Prior to Day 1 participants should abstain from alcohol for 72 hours prior to Day 1 visit and for 72 hours prior to every outpatient visit.
- 2 Participants should abstain from caffeine-containing foods and beverages for 24 hours prior to Day 1 and for 24 hours prior to every outpatient visit.
- 3 At the study Clinical Unit on Day 1, participants will receive a standard diet, which excludes all alcohol and caffeinated products. No additional food or beverages must be consumed while in the study Clinical Unit. Participants will not be asked to fast before the IMP administration and will be allowed to drink water to prevent dehydration from 45 minutes to 1 hour before dosing under medical supervision. Water and food will be allowed ad libitum from 1 hour after the start of dosing.
- 4 Participants are not required to abstain from food and drink intake prior to sample collection for safety assessments.
- 5 Participants should abstain from strenuous activity for 72 hours prior to Day 1 visit and 72 hours prior to each outpatient visit.
- 6 Participants should rest comfortably for 1 hour after IM administration.
- 7 Participants will be required to abstain from blood or plasma donation until 3 months after the final medical examination at the study follow-up.

For concomitant medication restrictions, please refer to Section [5.5](#).

4.2.1. Reproductive Restrictions

No genotoxicity studies have been conducted with AZD7442 and are not planned because this requirement is not applicable to biotechnology-derived large protein products. AZD7442 is a large protein molecule that is not expected to cross the nuclear or mitochondrial membranes to interact directly with DNA or other chromosomal materials.

4.2.1.1. Women of Non-childbearing Potential

Women of non-childbearing potential are defined as female participants who are permanently surgically sterilized or postmenopausal.

Permanent sterilization includes hysterectomy and/or bilateral oophorectomy and/or bilateral salpingectomy but excludes bilateral tubal ligation. Bilateral oophorectomy alone is acceptable only when the reproductive status of the woman has been confirmed by follow-up hormone level assessment.

Females are considered postmenopausal if they have had amenorrhea for at least 12 months or more following cessation of all exogenous hormonal treatments and without an alternative medical cause and the FSH level is in the postmenopausal range.

4.2.1.2. Women of Childbearing Potential

A woman is considered of childbearing potential, ie, fertile, following menarche and until becoming postmenopausal unless permanently sterile. Women of childbearing potential who are sexually active must agree to use, with their partner, an approved method of highly effective contraception from Day 1 to Day 361.

Highly effective contraception form of birth control, ie, a form of birth control with a failure rate of less than 1% per year when used consistently and correctly, which are allowed in this clinical study, are:

Methods that can achieve a failure rate of less than 1% per year when used consistently and correctly are considered as highly effective birth control methods. Such methods include:

- Combined (estrogen and progestogen containing) hormonal contraception associated with inhibition of ovulation:
 - Oral
 - Intravaginal
 - Injectable
 - Transdermal
- Progestogen-only hormonal contraception associated with inhibition of ovulation:
 - Oral
 - Injectable
 - Implantable
- Intrauterine device
- Intrauterine hormone-releasing system
- Bilateral tubal occlusion
- Vasectomized partner (only acceptable provided that partner is the sole sexual partner of the participant and that the vasectomized partner has received medical assessment of the surgical success)

- Sexual abstinence is defined as refraining from heterosexual intercourse during the entire period of risk associated with the study intervention. It is only acceptable if preferred and usual lifestyle of the participant.

In addition, a barrier method must also be used ie, condom (without spermicidal foam/gel/film/cream/suppository or fat- or oil-containing lubricants); or occlusive cap (diaphragm or cervical/vault caps) with spermicidal foam/gel/film/cream/suppository.

Pregnancy Testing

Women of childbearing potential can be included only after a negative highly sensitive serum pregnancy test. Additionally, urine pregnancy testing will be done as per the SoA ([Table 3-1](#)).

Pregnancy

If the participant becomes pregnant during the study this should be reported to the investigator. The investigator should also be notified of pregnancy occurring during the study but confirmed after completion of the study. The pregnancy will be followed, and the status of mother and/or child will be reported to the sponsor after delivery.

A pregnancy notification form and follow-up will be completed.

4.2.1.3. Male Participants

Restrictions for Male Participants

There is no information about effects that AZD7442 could have on the development of the fetus in humans.

All male participants should avoid the transfer of any fluids to a sexual partner by using a condom from the day of IMP administration (Day 1) up to 90 days following IMP administration. Female partners of male participants should be either of non-childbearing potential or should use a highly effective contraception form of birth control as mentioned in Section [4.2.1.2](#) above, from the day of IMP administration (Day 1) up to 90 days following IMP administration.

Sperm Donation

Male participants should not donate sperm for the duration of the study until after the last study Follow-up Visit.

Pregnancy

Participants will be instructed that if their partner becomes pregnant during the study this should be reported to the investigator. The investigator should also be notified of pregnancy occurring during the study but confirmed after completion of the study. In the event that a participant's partner is subsequently found to be pregnant after the volunteer is included in the

study, then consent will be sought from the partner and if granted any pregnancy will be followed and the status of mother and/or child will be reported to the sponsor after delivery.

A pregnancy notification form and follow-up will be completed.

4.3. Replacement of Participants

Participants who are withdrawn from the study after receiving any dose of IMP will not be replaced. Participants randomized in error or withdrawn prior to dosing may be replaced after consultation between the PI and AstraZeneca.

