- Section **6.3.7:** Text regarding SARS-CoV-2 testing updated.
- Section **6.5.1:** Renamed to **CCI** [REDACTED] and moved text from section 6.6: **CCI** [REDACTED] Samples under this section.
- Section **6.6:** Renamed to Immunogenicity Assessments and moved text from section 6.5.1: Collection of Pharmacodynamic Samples (regarding analysis of blood samples for determination of serum anti-AZD8895 and anti-AZD1061) under this section.
- Section **11.2.4.1:** Added requirement for last dose of anti-COVID-19 vaccine received prior to randomization, to be recorded in the EDC system.
- Section **12.1:** Replaced Principal Investigator with Medical Monitor and provided contact details for the Medical Monitor.
- Reference list updated.
- Additional minor formatting and grammatical corrections were made.
- Minor inconsistencies in the original protocol were clarified throughout the protocol.

PROTOCOL SYNOPSIS

Title of the Study

Phase I, Randomized, Open label, Three-arm, Single Dose, Parallel Group Study to Compare AZD7442 (AZD8895 + AZD1061) Pharmacokinetic Exposure Following Intramuscular Administration as a Co-formulation versus Administration from Two Separate Vials of the Individual Monoclonal Antibodies in Adult Healthy Participants

Study Center

This study will be conducted at a minimum of three different Clinical Units.

Study Rationale

The study will assess pharmacokinetic (PK) comparability between different formulations of AZD7442, which is a combination of two individual monoclonal antibodies (mAbs), AZD8895 and AZD1061. The materials to be assessed will be:

- A co-formulation of clonal cell line material of AZD8895 + AZD1061 mAbs as a single intramuscular (IM) injection from a single mixture,
- Individual formulations of clonal cell line material of AZD8895 and AZD1061 mAbs as separate sequential IM injections, and
- Individual formulations of cell pool material of AZD8895 and AZD1061 mAbs as separate sequential IM injections.

An open label, parallel group design has been chosen for this single dose PK comparability study.

Number of Participants Planned

Approximately 207 evaluable participants will be enrolled in this study.

Study Period

Estimated date of first participant enrolled: November 2021 (signing of informed consent)

Estimated date of last participant completed: Q3 2023

Study Objectives

The objectives of the study are:

Primary Objectives:

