3. STUDY DESIGN

3.1. Overall Study Design and Flow Chart

This study will be an open label, randomized, three-arm, parallel group, single dose, study in healthy participants (males and females), performed at multiple study centers.

A total of 207 evaluable healthy male and female participants will be randomized in a 1:1:1 ratio between the three treatment groups (69 participants per group). Each participant will receive AZD7442 as either a single IM dose (co-formulation; AZD8895 + AZD1061) from a single vial or as two separate IM doses of the individual mAbs (AZD8895 and then AZD1061) from two separate vials from either clonal cell line material or cell pool material as follows:

- **Treatment A:** 300 mg (total protein) AZD7442 as a single IM dose (co-formulation of 150 mg AZD8895 + 150 mg AZD1061) (clonal cell line material).
- **Treatment B:** 300 mg (total protein) AZD7442 as two separate IM doses of the individual mAbs (150 mg AZD8895 and then 150 mg AZD1061) (clonal cell line material).
- **Treatment C:** 300 mg (total protein) AZD7442 as two separate IM doses of the individual mAbs (150 mg AZD8895 and then 150 mg AZD1061) (cell pool material).

The product in Treatment Groups A and B is derived from material that originated from a clonal cell line, with a separate cell line, GMP cell bank, and manufacturing process for AZD8895 and AZD1061. The product in Treatment Group C is derived from material that originated from a non-clonal cell pool, with a separate pool of cells, GMP cell bank, and manufacturing process for AZD8895 and AZD1061. The clonal cell line is derived from a subpopulation of the respective cell pool, and there are no differences in antibody sequence between these cell banks. These materials have been demonstrated to be analytically comparable to each other. Refer to [Table 5-1](#) for details on the IMP.

Additionally, within each of the treatment groups, participants will be randomized 1:1:1 to one of the three injection sites:

- Lateral thigh,
- Gluteal dorsal,
- Gluteal ventral.

Further, participants will be stratified based on the body weight and vaccination status at randomization as follows:

[figure not shown]
- Body weight at randomization: < 70 kg; 70 to < 80 kg; and \geq 80 kg
- Anti-SARS-CoV-2 vaccination status at randomization: non-vaccinated or vaccinated (with one or more locally approved/authorized COVID-19 vaccine doses)

The study will comprise of:

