5.1.2. Procedures for Randomization

Upon completion of the randomization request form, the randomization list will be produced by the IRT vendor according to AZRand and participants will be randomized using IRT.

An IRT will be used for randomization to a treatment group and assignment of IMP kit numbers. A participant is considered randomized into the study when the investigator notifies the IRT that the participant meets eligibility criteria and the IRT provides the assignment of the IMP kit numbers to the participant.

Specific information concerning the use of the IRT will be provided in a separate manual.

The number of participant identifiers generated for the study will account for the required number of randomized participants per the sample size calculation (N = 207, see Section 11.4).

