5.2. Procedures for Handling Incorrectly Randomized Participants

Participants who fail to meet the inclusion criteria or meet any exclusion criterion should not, under any circumstances, be randomized into the study. There can be no exceptions to this rule.

Where a participant, who does not meet the selection criteria, is randomized in error and this is identified before dosing, the participant should be withdrawn from the study. If a participant is withdrawn prior to dosing they will be replaced.

If a participant, who does not meet the selection criteria, has been dosed before the error is identified, the participant should be advised to continue follow-up visits and safety assessments to ensure their safety. The investigator will inform the AstraZeneca Lead Physician of the error immediately.

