11.4. Determination of Sample Size

Preliminary analysis of PK data from the first-in-human study, D8850C00001, indicated that after an IM dose of IMP (separate AZD8895 and then AZD1061 doses) at a dose of 300 mg total protein, the CV% for Cmax of the individual mAbs, AZD8895 and AZD1061 were 35.6% and 38.5%, respectively, while the CV% for AUCs of both individual mAbs, AZD8895 and AZD1061 were < 36.4%. Therefore, assuming a mean ratio of 1 between comparators, 69 participants per group will provide at least 95% power to demonstrate comparability (90% CI contained within 0.8 and 1.25).

Table 11-1 Preliminary Pharmacokinetic data from Study D8850C00001

	AZD8895	AZD1061
Cmax	35.6%	38.5%
AUC0-last	29.1%	30.4%
AUC0-inf	26.8%	36.4%

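### 207 (69 per group) is both the evaluable target and the number randomised, with no allowance for non-evaluable participants, and the 95% power claim has little or no margin to absorb any

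*Protocol*

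**What the plan says.** **Size.** The protocol synopsis says "Approximately 207 evaluable participants will be enrolled in this study". Section 3.1 says "A total of 207 evaluable healthy male and female participants will be randomized in a 1:1:1 ratio between the three treatment groups", which is 69 per group. Section 5.1.2 ties the participant identifiers to the "required number of randomized participants per the sample size calculation (N = 207, see Section 11.4". One figure is thus used for both the evaluable and the randomised count.

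**Power.** Section 11.4 says "69 participants per group will provide at least 95% power to demonstrate comparability", assuming a mean ratio of 1. SAP Section 4.12 repeats this. Neither gives a dropout or non-evaluable allowance.

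**Replacement.** Section 4.3 says "Participants who are withdrawn from the study after receiving any dose of IMP will not be replaced". For participants randomised in error or withdrawn before dosing, it makes replacement optional, after consultation between the investigator and the sponsor. Section 5.2, on incorrectly randomised participants, is unconditional: "If a participant is withdrawn prior to dosing they will be replaced".

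**Who is evaluable.** The PK analysis set (Protocol 11.1.3, SAP 4.5.3) requires usable serum PK data and no important deviation thought to affect PK. Participants whose pre-dose concentration exceeds 5% of Cmax may also be excluded. Completion of Day 361 is not required. SAP 4.10.4 does not impute missing values.

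**The concern.** Whether a participant is evaluable is known only after dosing and sampling, so an evaluable count can equal a randomised count only if nobody becomes non-evaluable. Here nothing closes the gap: the list is not inflated, post-dose losses are not replaced, and missing parameters are not imputed. Follow-up lasts 360 days, and exclusions can also arise without dropout, through important deviations or a high pre-dose concentration.

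At stake is the accuracy of two statements: the evaluable size, and the power attached to it. If power at 69 were well above 95%, a few non-evaluable participants would not matter. So the question is how much margin there is.

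The two replacement passages also differ on whether replacing an undosed participant is optional or automatic.

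**Working it through.** **Inputs.** CVs from Protocol Table 11-1: Cmax 35.6% (AZD8895) and 38.5% (AZD1061); AUClast 29.1% and 30.4%; AUCinf 26.8% and 36.4%. True ratio 1, limits 0.80 to 1.25, 90% CI (two one-sided tests at 0.05), n = 69 per group, from Section 11.4. Assumption: the Table 11-1 CV is the residual CV.

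**Formulas.** Log-scale SD: s = sqrt(ln(1 + CV²)). Standard error of a two-group difference: se = s × sqrt(2/n). Power is the probability that both one-sided t tests (2n − 2 df) reject, integrated over the distribution of the estimated SD. Normal approximation at ratio 1: power ≈ 2Φ(ln 1.25/se − 1.645) − 1.

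**Step 1: the plan's own figure at n = 69.** For AZD1061 Cmax:
- s = sqrt(ln(1 + 0.385²)) = 0.3718
- se = 0.3718 × sqrt(2/69) = 0.0633
- ln 1.25/se = 0.2231/0.0633 = 3.525, and 3.525 − 1.645 = 1.880
- Approximate power 94.0%; exact 93.8%

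The exact values for the other parameters are:
- AZD1061 AUCinf 96.0%
- AZD8895 Cmax 96.7%
- AZD1061 AUClast 99.4%
- AZD8895 AUClast 99.7%
- AZD8895 AUCinf 99.9%

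The claim of at least 95% is reproduced for five of the six parameters. It is missed by about one point for AZD1061 Cmax, before any loss. Error df pooled over three arms (204) leave that figure at 93.8%.

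**Step 2: numbers needed for 95%.** AZD1061 Cmax 73 per group, AZD1061 AUCinf 66, AZD8895 Cmax 63. Against 69, the margins are −4, 3 and 6 participants per group.

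**Step 3: power as the evaluable number falls.** The loss rates are assumed, and n = 69 × (1 − loss), rounded down.

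| Assumed loss | n per group | AZD1061 Cmax | AZD1061 AUCinf | AZD8895 Cmax |
|---|---|---|---|---|
| 0% | 69 | 93.8% | 96.0% | 96.7% |
| 2% | 67 | 93.0% | 95.4% | 96.2% |
| 5% | 65 | 92.1% | 94.8% | 95.6% |
| 10% | 62 | 90.7% | 93.7% | 94.7% |
| 15% | 58 | 88.3% | 91.8% | 93.0% |
| 20% | 55 | 86.2% | 90.1% | 91.5% |

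Each column applies only to loss that removes that parameter. All figures are for one comparison and one parameter.

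**Step 4: which parameter late withdrawal threatens.** Cmax needs samples around the peak, and AUClast runs to the last quantifiable sample. AUCinf needs a terminal slope and an extrapolation. With the half-life of about 90 days in Protocol 3.3.2 and simple mono-exponential decline, the extrapolated share is about 2^(−180/90) = 25% if sampling stops at Day 181, and 2^(−90/90) = 50% at Day 91. AUCextr is calculated (Protocol 10.2, SAP 4.10.3), but no limit is set. Whether such a participant counts for AUCinf is therefore undefined.

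**The case against.** The strongest reply is that loss to follow-up is not non-evaluability. That is right. A reader might infer that 69 per group fails as soon as anyone is lost over the year, or that AUCinf needs a full year of samples. The documents support neither: the PK set does not require Day 361, and Protocol 5.7.1 and Table 3-2 plan an Early Termination visit with a PK sample where possible. What remains is that some dosed participants may still be non-evaluable, and the plan allows for none.

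The protocol also calls its 207 approximate in the synopsis, requires ability to complete follow-up (inclusion criterion 5), expects withdrawal to be uncommon (5.7.1), and generates additional random numbers (5.1). These make loss less likely or ease undosed replacement. None is a loss allowance, and the extra numbers are not tied to post-dose losses.

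A reader might also infer from Section 4.3 that arms could be selectively refilled in an open-label trial. The documents do not support this: codes are assigned in sequence and never reused (5.1), allocation is by IRT (5.1.2), and nothing lets a site choose a replacement's arm. Nor is it a natural reading that a participant dosed in error may be replaced, since the pre-dosing condition can govern the whole sentence and Section 5.2 keeps such participants in follow-up. What stands is the mismatch between optional and automatic replacement.

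Finally, the power effect is modest. That is also right.

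**Conclusion.** The point holds in limited form. The plan gives one number two meanings, and they agree only if no dosed participant becomes non-evaluable for a primary parameter.

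The shortfall from 95% should not all be put down to attrition. AZD1061 Cmax, the limiting parameter, is short with every participant evaluable. AZD1061 AUCinf falls short once more than 3 per group (3/69 = 4.3%) lack it. At an assumed 10% non-evaluable, the weakest parameter still has about 91% power. The design is therefore not seriously underpowered on these assumptions; the stated size and power are more favourable than the design guarantees.

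The figures rest on a true ratio of exactly 1, on Table 11-1 CVs standing in for residual CVs after covariate adjustment, and on loss rates that neither document supplies.

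**What to change.** - **Synopsis and Section 3.1:** describe 207 (69 per group) as the number randomised and dosed. Section 5.1.2 already speaks of randomised participants and needs no change on this point.
- **Section 11.4 and SAP 4.12:** restate power for each primary parameter, led by AZD1061 Cmax (about 94% at 69 per group), and over a stated loss range. For example, at 62 per group it is about 91% for AZD1061 Cmax and 94% for AZD1061 AUCinf. State what makes a participant evaluable for each parameter, AUCinf in particular.
- **Sections 4.3 and 5.2:** reconcile the two passages into one replacement rule that covers undosed participants only.

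The cost is wording in two documents and a slightly less favourable stated power. No participants are added. For comparison, actually delivering 69 evaluable per group at an assumed 10% loss would need 69/0.9 = 76.7, so 77 per group and 231 in total.
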